### a. Analysis of secondary outcomes

Secondary implementation outcomes will be analyzed at the level of the episode and will be modeled as per the primary analysis, using generalized linear mixed effects models, with appropriate links for binary and categorical dependent variables.

For example, for a binary outcome, the model has the form

$$\text{logit}(Y_{ijk}) = \mu + \alpha_i + \beta_j + X_{ij}\theta$$

Model parameters are similar to those in the primary outcome analysis.

Effectiveness outcomes and potential adverse effects will be analyzed at the level of the episode of MV. Binary and categorical effectiveness outcomes (mortality and discharge disposition) will be modeled per the primary analysis.

For MV duration, ICU length of stay, and hospital length of stay, because of a high mortality rate (~30%), we will model these outcomes as a composite with death using a “free days” approach. In other words, for duration of MV, for example, we will use ventilator-free days within 30 days, which will be calculated as the number of days a patient is alive and not on invasive mechanical ventilation for 30 days from the start of enrollment. We will use similar calculations for ICU-free days (alive and not admitted to the study ICU) and hospital-free days (alive and not admitted to the study hospital). For patients who are discharged alive and off the ventilator prior to 30 days, we will assume they are alive and off the ventilator for the remainder of 30 days. For patient who are discharged on the ventilator prior to 30 days, we will assume they remain on the ventilator for the remainder of 30 days. For patients who are discharged to hospice (home or facility), we will assume they have died upon the day of discharge.

We will explore the population where patients have multiple episodes of MV, as patients with multiple admissions may have higher risk of mortality. We will also examine the patient outliers in terms of MV

duration, ICU length of stay and hospital length of stay. Depending on the proportion, we may include multiple episodes into the study by creating a variable about the number of episodes.

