#### **d. Primary analysis**

The primary analytic approach will use a **modified intention-to-treat (mITT)** approach. We choose this approach because we have observed in preliminary studies in the study ICUs that some patients will start MV and receive MV orders prior to ICU admission, and because of the constraints of the EHR to deploy the strategies, such episodes will not be eligible to be exposed to the intervention. Because ICUs differ in their percentages of patients who will and will not be eligible for exposure to the strategies, and these patient groups may be systematically different, in the primary analysis, we will limit the population to patients who receive a new MV order within 72 hours of enrollment (the time of the start of MV in the ICU).

The unit of analysis for primary study outcome (and all implementation outcomes) will be the episode of mechanical ventilation.

- Patients may have multiple episodes of MV if the patient is ventilated multiple times. We will include only the first eligible episode during a hospital admission for the primary analysis. We will calculate the proportion of patients who receive multiple episodes or multiple admissions. We expect the proportion will be very small, based on prior data from study ICUs.

The primary comparisons of interest will be:

- strategy A vs. strategy B
- strategy A vs. control
- strategy B vs control
- strategy A vs. strategy A combined with strategy C
- strategy B vs. strategy B combined with strategy C

Secondary comparisons of interest are control versus A + C, control versus B + C, and control versus C alone among patients who are not exposed to the order panel strategies (i.e., in the ITT but not mITT population).

We will use a linear mixed-effects model for primary analysis. The structure of the model is as follows:

$$Y_{ijk} = \mu + \alpha_i + \beta_j + X_{ij}\theta + e_{ijk}$$

where  $Y_{ijk}$  denotes the percentage from individual  $k$  at time  $j$  from cluster  $i$ ;  $\alpha_i$  is a random effect for cluster  $i$ ;  $X_{ij}$  is the treatment indicator for cluster  $i$  at time  $j$ ,  $\theta$  is the treatment effect and the residual is  $iid$  with  $e_{ijk} \sim N(0, \sigma_e^2)$ . Since the intervention occurs over time, the proportion of clusters exposed to the intervention gradually increases. We will include step as a fixed effect ( $\beta_j$ ) in the model to adjust for the potential confounding factor from calendar time.

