## IX. Sensitivity analyses

- a. **Time effect might differ across clusters:** To account for the possibility that the time effect might not be the same for all clusters, we will add a random interaction term for the cluster-time combination  $\varphi_{ij}$ .
- b. **Treatment effect might differ across clusters:** To evaluate the possibility of treatment-effect heterogeneity, we will add a random interaction term  $X_{ij}\tau_i$  which allows different treatment effects for different clusters.
- c. **Exclusion of subsequent MV episodes in patients with multiple MV episodes may lead to bias estimates of effect:** To address potential bias of excluding subsequent episodes of MV among patients who undergo multiple episodes, we will repeat the primary analysis including all eligible episodes of MV.

d. **ICU may be a potential confounder.** Because the study ICU may itself be a potential confounder, we will repeat analyses modeling the study ICU as a fixed effect.

In order to preserve an overall family wise error rate of 0.05, we will pre-specify a type I error rate threshold for the comparison of A vs. B at 0.025, and will estimate the Holm thresholds for the remaining comparisons by ordering unadjusted p-values (from the smallest to largest), and then calculating it as 0.025 divided by n remaining contrasts.

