**Table 2 Secondary outcome measures**

| Implementation Outcomes  | Variable coding | Definition  |
|---|------------------------|--|
| 
 
Total duration of exposure to tidal volume >8 cc/kg and >10 cc/kg IBW
 
 | Continuous             | In hours; exclude time on minimal settings; report for first 72h after enrollment and for entire duration of MV episode within a study ICU   |
| 
 
Initial tidal volume administered
 
   | Continuous             | In cc/kg IBW; exclude time on minimal settings; report the first documented tidal volume at or after the time of enrollment  |
| 
 
Plateau pressure (Pplat) >30cm H2O at time 0 and time 24h
 
                | Binary                 | Time 0 is the earliest measure between 0 and 6h; time 24 is the measure between 18h and 30h that is closest to 24h and earliest if there are two measures of the exact same distance from 24h (e.g., one before and one after) |
| Effectiveness Outcomes   |                        |  |
| 
 
Hospital mortality
 
  | Binary                 | Vital status at hospital discharge   |
| 
 
Hospital discharge disposition
 
  | Categorical            | To be collapsed into 4-6 categories  |
| 
 
Duration of MV
 
  | Continuous             | From time of enrollment to end of MV in study ICUs, up to 30 days  |
| 
 
ICU length of stay
 
  | Continuous             | From time of enrollment to end of admission to enrolling ICU, up to 30 days  |
| 
 
Hospital length of stay
 
   | Continuous             | From time of enrollment to time of hospital discharge, up to 30 days   |
| Potential Adverse Effects  |                        |  |
| 
 
Early deep sedation
 
   | Continuous             | Proportion of time during the first 72 hours of mechanical ventilation that patients were alive, in the ICU, and with Richmond Agitation-Sedation Scale (RASS) of -3 to -5   |

|  |            |  |
|--|------------|--|
| • Average sedation intensity within the first 72 hours                           | Continuous | Average RASS value, weighted by duration of time at that value   |

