### **b. Timing of analysis and adjustment of significance level**

Two interim analyses will be conducted after approximately 9 months and 18 months after trial launch (one-third and two-thirds of the trial duration, respectively) of two study outcomes: (1) fidelity to LPV (primary outcome, as specified above), and (2) in-hospital mortality. All interim analyses will be performed at the level of an episode of mechanical ventilation. For the open portion of the DSMB meeting, we will summarize data for the entire study population in aggregate, including patient characteristics, key patient outcomes, and the primary study outcome (percentage of time during the first 72h of MV in the ICU that the patient has tidal volume less than or equal to 6.5cc/kg IBW). We will also report adverse event rates among in aggregate.

To evaluate mortality by group, we will first report unadjusted mortality rates by group, and then proceed in a stepwise fashion with up to three risk-adjusted models:

- Model 1: We will use a generalized linear mixed effects model to estimate unadjusted mortality accounting for design issues; that is, including a random effect for ICU, a fixed effect for study group assignment, and a fixed effect for step (to account for potential confounding from calendar time).
- Model 2: We will use a generalized linear mixed effects model to preliminarily test whether study group assignment is associated with mortality after risk adjustment. As in the above model, we will include a random effect for ICU, a fixed effect for study group assignment, and a fixed effect for step (to account for potential confounding from calendar time). Given variability in case mix, we will also include the following covariates for risk adjustment: age, sex, race, source of admission to the hospital, Elixsauser score and LAPS2 score on the day of study enrollment.

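### SAP X.a leaves open, with no threshold or model form, adding repeat ventilation episodes and an episode-count variable to the analyses of mortality and free days

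*SAP*

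**What the plan says.** SAP V.d makes the ventilation episode the unit of analysis and then restricts it: "We will include only the first eligible episode during a hospital admission for the primary analysis". It expects repeats to be very rare but gives no figure. Its model has one random effect, for the cluster. It also limits adjustment, in all analyses, to characteristics already present before the patient becomes eligible.

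SAP X.a turns to the effectiveness outcomes: "Effectiveness outcomes and potential adverse effects will be analyzed at the level of the episode of MV". For two of them it refers back to V.d: "Binary and categorical effectiveness outcomes (mortality and discharge disposition) will be modeled per the primary analysis". The free-day paragraph does not repeat that link. The section then closes with the open option: "Depending on the proportion, we may include multiple episodes into the study by creating a variable about the number of episodes". It does not say:

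- what proportion would trigger the option;
- whether each episode becomes a row;
- whether the variable is a total or a running number;
- how the variable enters the model;
- which outcomes are meant.

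The outcomes themselves are defined per admission or per patient. Table 2 defines hospital mortality as "Vital status at hospital discharge". X.a defines ventilator-free days as "the number of days a patient is alive and not on invasive mechanical ventilation for 30 days from the start of enrollment".

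Two other places mention episodes. Sensitivity analysis IX.c says "we will repeat the primary analysis including all eligible episodes of MV", which concerns fidelity. SAP XIV.b says "All interim analyses will be performed at the level of an episode of mechanical ventilation", without repeating the first-episode limit.

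**The concern.** Fidelity can be measured separately in each episode. Death, disposition and free days cannot. All episodes within an admission share one vital status at discharge. A reintubation within 30 days of enrollment already lowers the free-day value of the first record, so a second row would count it again in an overlapping window.

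The proposed variable raises a separate problem. The total number of episodes is known only after the strategy has acted, and the strategy may influence it. Holding it fixed blocks any route from strategy to death that passes through extubation failure.

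The choice would also be made after the proportion of repeats has been seen. At stake is whether the final mortality and free-day comparisons estimate a total effect per admission, as the default would, or something harder to interpret.

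**Working it through.** The plan states no figure on this point, so there is none to reproduce. The check takes each plain reading of the sentence and asks what it does to a mortality comparison.

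**Inputs from the documents.** mITT sample 5,100 (SAP XII.a). Baseline mortality 25% (SAP XII.b; X.a mentions about 30% in passing). Expected deaths: 5,100 × 0.25 = 1,275.

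**Assumed, because the documents give no figures.** Share of admissions with a repeat episode 2% to 15%; mortality in those admissions 25% to 40%; one extra episode each.

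**Step 1: repeated deaths, one row per episode.** With repeat share q and mortality m among repeats, rows = 5,100 × (1 + q) and counted deaths = 1,275 + 5,100 × q × m.

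| q | Rows | Counted deaths, m = 25% | Counted deaths, m = 40% |
|---|---|---|---|
| 2% | 5,202 | 1,300 | 1,316 |
| 5% | 5,355 | 1,339 | 1,377 |
| 10% | 5,610 | 1,402 | 1,479 |
| 15% | 5,865 | 1,466 | 1,581 |

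With no patient-level term, the variance of the mortality proportion is understated. Setting the ICU effect aside and taking equal mortality in both kinds of admission, the ratio of true to naive variance is (1 + 3q)/(1 + q). That is 1.06/1.02 = 1.04 at 2% and 1.45/1.15 = 1.26 at 15%. With 40% mortality in repeats it is 1.05 and 1.34.

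**Step 2: harm acting wholly through reintubation.** Take 2% reintubated under control, 4% under a strategy, and 40% mortality if reintubated. Mortality without reintubation is then (0.25 − 0.02 × 0.40)/0.98 = 24.69% in both groups.

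- One record per admission: 25.00% versus 0.96 × 24.69% + 0.04 × 40% = 25.31%, an excess of 0.31 points.
- One row per episode, no count variable: (0.98 × 24.69% + 2 × 0.02 × 40%)/1.02 = 25.29% versus (0.96 × 24.69% + 2 × 0.04 × 40%)/1.04 = 25.87%, an excess of 0.58 points.
- Adjusted for total count: within each level of the count the groups have equal mortality, so the excess is 0.

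**Step 3: the readings side by side.** The column for 10% versus 15% uses the same formulas. The running-number row comes from linear fits to the expected cell counts.

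| Reading | Deaths repeated? | Excess, 2% vs 4% | Excess, 10% vs 15% |
|---|---|---|---|
| One record per admission (default) | No | +0.31 | +0.83 |
| One record, total count as covariate | No | 0.00 | 0.00 |
| Row per episode, no count | Yes | +0.58 | +1.32 |
| Row per episode, total count | Yes | 0.00 | 0.00 |
| Row per episode, running number | Yes | +0.30 | +0.74 |

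Each reading other than the default either repeats deaths or conditions on reintubation. Only a row per episode with a total count does both.

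**Step 4: fit with the rest of the plan.** The default already admits one episode from every admission, so the rows the option would add are repeats within an admission, which share one death. A total count is not known before eligibility, so it conflicts with the covariate rule in V.d. Protocol 7.2.1 also assigns the study group by the ICU's status when ventilation starts. An admission with two episodes either side of a transition could therefore place one death in two groups.

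**The case against.** The strongest reply is that the sentence is permissive and the default is already right. First episode per admission is fixed in V.d, and mortality and disposition are modelled in the same way. In V.d, naming the episode as the unit of analysis sits beside a first-episode limit, so the same phrase in X.a and XIV.b does not by itself admit repeats. This stands, and a reader who infers that the SAP plans to count deaths several times goes beyond the text.

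Second, milder readings exist. One row with a count repeats no death, and a running number keeps most of the harm estimate. The paragraph's own rationale speaks of patients with multiple admissions, and separate admissions have separate vital status. This also stands, so the two faults should not be presented as certain or as always occurring together. It does not rescue the sentence, because each reading keeps one of the faults.

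Third, a reader might infer that the mortality stopping rule adjusts away harm. The documents do not support that. The option sits in X.a, and the interim covariates listed in XIV.b (age, sex, race, admission source, a comorbidity score and LAPS2) include no episode count. The excesses illustrated here are also well below the 5-point trigger for further interim analysis. What remains for the interim is only that its first-episode limit is left to inference.

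Fourth, the zero is built in by assuming that all harm runs through reintubation. Direct harm would survive the adjustment. That is correct.

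Finally, IX.c is a labelled sensitivity analysis of fidelity, which each episode has in its own right. No outcome is double-counted there, and a missing patient term mainly affects standard errors.

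**Conclusion.** The point holds as a flaw in an optional analysis. X.a keeps a data-dependent choice open for outcomes that belong to the admission, and no plain reading of it improves on the default. Used with a row per episode, it would enter one admission's outcome more than once. Used with a total count, it would adjust for a post-exposure variable and could remove an effect acting through reintubation.

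The likely size is modest. At an assumed 2% versus 4% reintubation, 0.31 points becomes 0.58 or 0; at 10% versus 15%, 0.83 becomes 1.32 or 0. The mortality differences the SAP powers for are 9 points (25% to 16%) and, as revised, 11 points (25% to 14%). These illustrations rest on assumed reintubation shares, 40% mortality after reintubation, one extra episode each, and no direct effect. The case for changing the wording does not depend on them. It follows from the outcome definitions and from the SAP's own covariate rule.

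**What to change.** - Delete the closing sentence of X.a on including multiple episodes.
- State there that mortality, disposition and all free-day outcomes use one record per admission, the first eligible episode.
- State in XIV.b that the interim mortality analysis uses the same record. SAP XII.a already refers to the first interim analysis in the past tense, so for that look the statement would document which record was used.
- Report the number of repeat episodes by study group as a descriptive outcome, and do not use it as a covariate.
- Keep IX.c as a sensitivity analysis of fidelity, and add patient-level clustering, for example a patient random intercept.

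The cost is SAP wording only. No new data are needed. The 5,100 projection is for the primary population, which already takes the first episode per admission, so power is unaffected.

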## **XI. Approach to missing data**

Based on preliminary analyses of missingness within a retrospective cohort of MV patients admitted to 11 of 12 study ICUs, we propose the following approaches to missing data, based on specific data elements:

- Missing or erroneous value for ideal body weight: Less than 5% of patients in a retrospective patient cohort including 11 of 12 study ICUs have either missing or erroneous data for patient height, which results in a missing or erroneous value of ideal body weight. Because the EHR-based implementation strategies will not function for patients with missing data for height (i.e., there will be no pre-populated value for tidal volume, or threshold to trigger the accountable justification prompts), we will exclude these patients from the primary analysis and will report the percentage of missingness in the results. We will also examine if there is any pattern of erroneous data.
- Missing data for ventilator settings: Ventilator flowsheet data are entered at variable intervals, depending on clinical circumstances (e.g., if a patient's settings are changed) and routine practice (e.g., the ICU documentation standards). Therefore, there are no regular intervals during which ventilator flowsheet data will be entered. At any given time point, some or all relevant ventilator data may or may not be entered by a respiratory therapist or nurse. If ventilator data settings are partially missing for a given time (e.g., one setting or parameter is documented but others are not at a certain time), we will use single imputation, carrying forward data from the prior time of documentation for any relevant parameters that are missing. We choose this strategy because we suspect that if a setting or parameter is not documented at a subsequent time, then that setting or parameter is unlikely to have changed from prior (i.e., a change in a setting or parameter would typically prompt documentation).
- Missing or erroneous data for potential confounders, including severity of illness measures: In our previous experience working with data from the retrospective cohort, we anticipate minimal missingness for variables that will be included in the severity of illness measure (LAPS2). In the rare event that we do have missingness for a parameter, we will use single imputation of a normal value for that parameter, as is the common approach in calculation of severity of illness measures. This strategy would bias the results towards the null. We will report percentage of missingness and discuss the risk of bias in the limitations.

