3.7 Interventions

ICUs, which have individual practices for identifying eligible patients and administering LPV, will sequentially implement two of three EHR-based strategies to further promote LPV utilization among all MV patients. Strategies will be rolled out via a stepped-wedge design. Study ICUs will be randomly assigned to first receive either a **default order set (Strategy A)** or **physician-targeted accountable justification strategy (Strategy B)**. Six months after Strategies A and B are implemented, ICUs will add on an **RT-targeted accountable justification strategy (Strategy C)**.

Strategy A: Default order set for MV

With the default order set strategy, a physician will see a different order panel to order mechanical ventilation settings than the current usual state. In this intervention order panel, the ventilation mode will be pre-selected to be assist-control, volume-cycled; and the tidal volume will be pre-populated via an automatic calculation of 6 cc/kg of the patient's ideal body weight (as determined by each patient's height and sex, which are entered into the EHR during every hospital admission). The physician will have the option to opt out of any of the pre-specified settings with one click.

Strategy B: Physician-targeted accountable justification of MV orders

In this strategy, the order panel will remain nearly identical to the current state, with no pre-specified settings. However, if a physician enters an order for a set tidal volume that is greater than 6.5 cc/kg ideal body weight, the physician will be required to enter a reason for choosing a setting inconsistent with LPV into a free text box. This box would instruct them to provide a reason for deviation from LPV settings and will inform them that their response will be maintained in the medical record. The physician will not be able to proceed with entering the MV order until after a response is entered.

Strategy C: RT-targeted accountable justification of initial MV settings

In this strategy, if an RT enters a set tidal volume value greater than 6.5 cc/kg into the flowsheet, he/she will receive a prompt to enter an explicit reason for deviating from LPV settings, similar to the physician-targeted accountable justification strategy.

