3.8 Data Collection

All research patient data for this pragmatic clinical trial will be captured electronically via the UPHS EHR. Thus, consistent with the goals of a pragmatic trial, there are no research personnel located onsite at each study hospital. Instead, outcomes data will be restricted to data elements that are routinely collected in the course of providing routine clinical care and extracted from the UPHS EHR.

This study also seeks to understand how the implementation strategies function in the context of different clinician and environmental factors, including additional barriers and facilitators of LPV

utilization. During the two months after the implementation strategy rolls out in each ICU, we will perform semi-structured interviews of all physicians and RTs who staff study ICUs. All interviews will be completed by a single research coordinator, who will be trained in the conduct of semi-structured interviews. The interviews follow a guide and begin with neutral, open-ended questions, followed by questions that arise from clinicians' responses, with the interviewer pursuing themes, probing for further details, and seeking clarification and elaboration when appropriate. All interviews will be audio-recorded with the participants' consent and professionally transcribed. No identifiable information will intentionally be collected but may be recorded during the interview. Any identifiable information in interviews will be removed in transcription.

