## V. Primary outcome and analytic method

### a. Primary outcome

The primary outcome variables will be (1) **fidelity** to LPV, measured by the percentage of time in the first 72 hours of mechanical ventilation that a patient is exposed to tidal volume  $\leq 6.5$  cc/kg ideal body weight and (2) **sustainability** of the effects of the implementation strategies, measured as the percentage of time in the first 72 hours of MV that a patient is exposed to tidal volume  $\leq 6.5$  cc/kg ideal body weight among MV patients each month during 6 months after the study monitoring period ends.

We will consider episodes separated by less than or equal to 2 hours as a single episode. We will count the period of time that a patient is extubated as if the patient is on minimal settings, and will therefore subtract that period of time from the denominator of the primary outcome variable (if it falls in the first 72 hours).

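### Strategy C prompts on charting of high tidal volumes, the likely source of the primary outcome; with carry-forward, unrecorded high values would favour C, and no planned analysis would show it

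*SAP*

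**What the plan says.** - **Trigger.** Under Protocol 3.7 the Strategy C prompt appears "if an RT enters a set tidal volume value greater than 6.5 cc/kg into the flowsheet". What sets it off is the act of charting. The Protocol Summary describes a pop-up asking for a free-text rationale.
- **Outcome.** SAP V.a measures fidelity as the "percentage of time in the first 72 hours of mechanical ventilation that a patient is exposed to tidal volume" at or below 6.5 cc/kg ideal body weight. (The protocol states the complement, time above 6.5.)
- **Source.** Protocol 3.8 limits outcome data to elements "routinely collected in the course of providing routine clinical care and extracted from the UPHS EHR". No separate ventilator record is described.
- **Charting.** SAP XI says that "there are no regular intervals during which ventilator flowsheet data will be entered", and that at any time point "some or all relevant ventilator data may or may not be entered by a respiratory therapist or nurse".
- **Missing values.** A partly charted time point is completed by single imputation, "carrying forward data from the prior time of documentation for any relevant parameters that are missing", on the ground that "a change in a setting or parameter would typically prompt documentation". Protocol 7.3 has the same rule.
- **Use.** A vs A+C and B vs B+C are two of the five primary comparisons (SAP V.d). C is also the only exposure in the subgroup of ITT patients outside the mITT population (SAP VIII).
- **Checks.** The four sensitivity analyses in SAP IX cover cluster-specific time effects, treatment heterogeneity, repeat episodes and ICU as a fixed effect. SAP XI promises to report missingness for height and for severity variables, but not for ventilator settings.

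**The concern.** Carry-forward is harmless if an unrecorded setting really is unchanged. Strategy C gives an RT a reason to leave one kind of value unrecorded, namely a tidal volume above the outcome threshold. If the other settings are charted, tidal volume is left blank and the last charted value was at or below 6.5, the rule scores the following time as adherent. Control, A and B alone carry no such disincentive at the flowsheet, so the error would differ between conditions and would run towards C.

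At stake are the contrasts involving C: the two primary ones, the secondary comparisons of control with A+C, B+C and C alone, and the C-only subgroup. In each, a change in charting could be read as a change in ventilation.

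**Working it through.** The plan gives no figure for this, so there is none to reproduce. The check sizes the possible artefact from the plan's own outcome distribution.

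**Inputs.** From SAP XII.b: baseline mean 45%, SD 45%. Assumed: 18 tidal-volume entries per 72 hours, the first always charted, and a share *b* of high entries left blank at random, with *b* from 5% to 75%.

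**Step 1: when carry-forward matters.** A blank after a high value stays high, so an episode that is high throughout gains nothing. Only blanks that follow a low value are miscounted.

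**Step 2: how much mixing the SD allows.** For an outcome bounded by 0 and 1 with mean 0.45, the largest possible variance is 0.45 × 0.55 = 0.2475. The SAP's variance is 0.45² = 0.2025, and 0.2025 / 0.2475 = 82% of that maximum. Most episodes are therefore nearly all low or nearly all high, and low-to-high changes are uncommon.

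**Step 3: approximate formula.** Let *p* be an episode's share of low time. If successive entries are independent given *p*, a charted entry is low with probability p / [1 − b(1 − p)], and the expected gain is b·p(1 − p) / [1 − b(1 − p)]. For small *b* this is close to b·p(1 − p). Averaged over episodes, p(1 − p) equals mean × (1 − mean) − variance = 0.2475 − 0.2025 = 0.045. The gain is then about 4.5 points × *b*:
- b = 5%: 0.05 × 4.5 = 0.2 points
- b = 10%: 0.10 × 4.5 = 0.45 points
- b = 20%: 0.20 × 4.5 = 0.9 points

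For larger *b* the denominator matters and simulation is needed.

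**Step 4: simulation.** Episodes were drawn from a beta distribution with this mean and SD. The lower ends below arise when high and low entries come in runs, the upper ends when successive entries are independent.

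| High entries left blank | Apparent gain, points |
|---|---|
| 5% | 0.04 to 0.2 |
| 10% | 0.1 to 0.45 |
| 20% | 0.2 to 0.9 |
| 50% | 0.7 to 2.8 |
| 75% | 1.8 to 5.5 |

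The upper ends at 5% to 20% agree with Step 3.

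**Step 5: sensitivity.** A simpler two-state model with few setting changes gave about 1, 2 and 6 points when 25%, 50% and 75% of high entries were blank. With frequent changes it gave about 3, 7 and 17, but frequent switching pulls episode percentages towards the middle and is hard to square with an SD of 45%.

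**Step 6: reference level.** The primary C contrasts start from fidelity under A or B, not control. If A or B reached the 70% used in the power calculation, high time would fall from 55% to 30%, leaving less to miscount. The documents give no SD at that level, so Step 4 cannot be repeated there.

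**The case against.** The strongest reply is that several links are inferred.

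- The documents do not say that the outcome is computed from the prompted set-volume field, or whether it is set or delivered volume. This stands. The shared threshold and the flowsheet missing-data rule make it a reasonable inference, no more.
- Nothing documents that RTs would chart less. The protocol states that Strategy B blocks the order until a reason is entered; it states no such block for C, so the incentive is weaker. This stands, although Protocol 7.2.1 itself allows that clinicians may get round the nudges.
- Strategy C is titled as concerning initial settings, and at a first entry there may be no lower value to carry forward. This partly stands: the plan has no rule for time before the first charted value, and dropping that time would also favour C.
- The rule covers partly charted time points only. This stands: fully uncharted intervals have no stated rule.
- Nurses also chart, which may dilute the effect, and plateau pressure above 30 at 0 and 24 hours (SAP X, Table 2) is an outcome that C does not prompt on. Both help, but neither measures whether charting of tidal volume changed.

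A reader might infer a much larger artefact by applying 5% to 20% to all time above threshold: 55 × 0.05 to 55 × 0.20 = 2.75 to 11 points. The documents do not support this. Those percentages would be time already miscounted as low, not entries left blank, and the SAP's SD implies that most high time is in episodes with little or no low value to carry forward.

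**Conclusion.** The gap is real but conditional. If RTs selectively leave high values blank under C, the missing-data rule moves A vs A+C and B vs B+C towards C, and the plan has no means of seeing it. On the SAP's mean and SD and the assumed charting pattern, the artefact stays below 1 point up to 20% blank, and reaches about 0.7 to 2.8 points at 50% and 1.8 to 5.5 at 75%. Avoidance clustered in particular patients or shifts could add more than these random-blank figures.

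Two stronger readings do not follow. One is that any observed effect of C is a charting artefact: the documents contain no evidence on charting under C. The other is that the trial's main result is compromised: A and B act on the order panel, so A vs control, B vs control and A vs B are not directly affected, and both stated primary hypotheses (SAP V.b) concern A and B only.

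The case for acting is that the checks are cheap and leave the primary model unchanged.

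**What to change.** Add to SAP IX, for the contrasts involving C:

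1. Analyse tidal-volume entries per ventilated hour, and the share of charted time points with tidal volume blank, by condition, using the primary model structure.
2. Repeat the primary analysis counting as above 6.5 all time that rests on a carried-forward tidal volume at or below 6.5, that is, from a blank time point to the next charted tidal volume. State in advance whether this applies in every condition or only under A+C and B+C; the latter is the stricter bound. Do not instead remove that time from numerator and denominator: if high time is what goes unrecorded, removal also inflates fidelity under C, and in simulation it did so as much as carry-forward or more.
3. If the role of the person charting can be extracted, repeat with nurse-entered values. The documents do not confirm that it can.

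Report these beside the primary C contrasts, and qualify any claim for C if charting falls under C or the effect disappears under (2). Because (2) also recodes low settings that truly did not change, a lost effect would mean that an artefact cannot be excluded, not that one occurred.

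SAP V should also name the tidal-volume field used for the outcome.

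Cost: extra analysis of flowsheet data, with lower precision in (3).
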